Treatment Complete	Treatment Complete is defined as any subject that received 100% of the Sonendo GentleWave Treatment (Treatment) over the course of no more than two visits.
Definition of Sonendo GentleWave System Treatment	The Sonendo GentleWave System Treatment is defined as beginning when LuxaBite ® (DMG) or a Sonendo Tooth Cap is placed until 100% completion of the Sonendo GentleWave System. All other procedures will be categorized as traditional RCT procedures.
Indication	The Sonendo GentleWave System is intended to prepare, clean, and irrigate 1 st and 2 nd molar teeth indicated for root canal therapy.
Primary Effectiveness Endpoint	Subject teeth in the Treatment Complete cohort that are healed or are healing at the twenty-four month follow-up visit.
	Healed is defined by absence of a radiographic indication of apical periodontitis (PAI <3) and absence of clinical signs and symptoms.
	Healing is defined by a reduction of radiolucency (if radiolucency is present at Baseline) and/or reduction of clinical signs and symptoms (if clinical signs and symptoms are present at Baseline)
	Secondary analysis will be completed after all Treatment Complete subjects complete the 12 month follow-up. Additional analysis may occur.
Primary Safety Endpoint	Incidence of device related adverse events as defined by perforation, instrument separation, root fracture, sodium hypochlorite accident, or Gutta Percha extrusion, as related to the device for the Treatment Complete cohort.

Secondary Endpoint(s)	The following outcomes will be assessed:
	1. McGill Short Form Pain Questionnaire
	2. Gracely Descriptor Differential Scale (DDS)
	3. Patient Satisfaction Survey
	4. AAE Case Difficulty Assessment
	5. Soft Tissue Lesions
	6. Swelling
	7. Root Canal Therapy Retreatment
	8. Treatment Time
	9. Procedure Time
	10. Periapical Index (PAI) analyzed utilizing
	radiographic analysis by independent reviewer
	11. Cone Beam Computed Tomography (CBCT) Sub-Set Evaluation
	12. Additional Radiographic Analysis may be completed
Pre-Procedure Inclusion	1. The patient is 18 to 75 years of age
Criteria	2. The subject tooth is indicated for root canal therapy
	3. The subject tooth is a 1 st or 2 nd molar
	4. The patient is mentally and physically able and willing to fully comply with this protocol, including adhering to the follow-up schedule and completing forms and questionnaires
	5. Signed Informed Consent Form

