#### 5.1 Pre-Procedure Inclusion Criteria

- 1. The patient is 18 to 75 years of age
- 2. The subject tooth is indicated for root canal therapy
- 3. The subject tooth is a 1st or 2nd molar
- 4. The patient is mentally and physically able and willing to fully comply with this protocol, including adhering to the follow-up schedule and completing forms and questionnaires
- 5. Signed Informed Consent Form

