#### 7.4.4 Baseline Exam

The PI will perform the following standard of care assessments and evaluations prior to the procedure, if they were not already completed:

- 1. Medical and Dental History and Exam
  - a. Medical History: Only those histories related to endocrine/metabolic, hematologic, musculoskeletal, and immunological will be collected for the study.
- 2. Medication Regime: Only prescribed herbal or over the counter systemic antibiotics, analgesics, and anti-inflammatory medications taken during the duration of the study (24 months post procedure) and the prior three months will be documented for this study.
  - Any antibiotics, analgesics or anti-inflammatory medications provided intraprocedure by the PI during the Baseline and Procedure Visits will be collected for the study and will be documented on the Concomitant Medication Log.
  - Any antibiotics, analgesics and anti-inflammatory medications should be collected if prescribed or provided post Procedure Visit, and at all Follow-ups.
- 3. McGill Short Form Pain Questionnaire: The McGill Pain Questionnaire (MPQ) is one of the most widely used tests for the measurement of pain. It provides information on sensory, affective, and evaluative dimensions of pain experience and is capable of discriminating among different pain problems.

- 4. Gracely Descriptor Differential Scale (DDS): This scale is an intensity and unpleasantness scale. The scale includes both verbal and numeric characteristics.
- Diagnostic Radiographic Analysis: Periapical (PA) Parallel Radiograph, showing the periapical region surrounding the subject tooth should be collected for each visit. Additional radiographs completed as necessary by the PI will be collected for the study.
- 6. Periapical Index (PAI) Score analyzed by independent reviewer Up to three (3) independent reviewers will be provided radiographs in order to complete the PAI scoring. Independent reviewers will be blinded to the site, subject, and visit when completing the PAI score. This is being done to eliminate bias.
  - Score of 1: Normal
  - Score of 2: Small changes in bone structure
  - Score of 3: Changes in bone structure with some mineral loss (bone loss)
  - Score of 4: Periodontitis with well-defined radiolucent area (apical periodontitis)
  - Score of 5: Severe Periodontitis with exacerbating features (apical periodontitis)

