  - Delayed: A painful sensation is felt after an initial delay
- vi. Root Resorption
- vii. Furcation Involvement/Furcation Defect
  - Class I: The furcation can be probed, but not to a significant depth.
  - Class II: The furcation can be entered into but cannot be probed completely through to the opposite side.
  - Class III: The furcation can be probed completely through and through.
  - Class IV: The furcation can be probed through and through, and recession reveals a visible furcation.
- 9. Endodontic Assessments including:
- a. Pulp Diagnosis:
  - Normal Pulp: A clinical diagnostic category in which the pulp is symptomfree and normally responsible to pulp testing.
  - Reversible Pulpitis: A clinical diagnosis based on subjective and objective findings indicating that the inflammation should resolve and the pulp return to normal.
  - Symptomatic Irreversible Pulpitis: A clinical diagnosis based on subjective and objective findings indicating that the vital inflamed pulp is incapable of healing. Additional descriptors: lingering thermal pain, spontaneous pain, referred pain.
  - Asymptomatic Irreversible Pulpitis: A clinical diagnosis based on subjective and objective findings indicating that the vital inflamed pulp is incapable of healing. Additional descriptors: no clinical symptoms but inflammation produced by caries, caries excavation, trauma.
  - Pulp Necrosis: A clinical diagnostic category indicating death of the dental pulp. The pulp is usually nonresponsive to pulp testing.
  - b. Periradicular Tests (Percussion and Palpation):
    - None (-): No discomfort at all.
    - Mild (+): Little discomfort, but may be noticeable by the patient.
    - Moderate (++): Some noticeable discomfort.
    - Severe (+++): Definitive discomfort.
  - c. Periradicular Diagnosis:
    - Normal Apical Tissue: Teeth with normal periradicular tissues that are not sensitive to percussion or palpation testing. The lamina dura surrounding the root is intact, and the periodontal ligament space is uniform.
    - Symptomatic Apical Periodontitis: Inflammation, usually of the apical periodontium, producing clinical symptoms including a painful response to biting and/or percussion or palpation. It might or might not be associated with an apical radiolucent area.

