# 7.17 Follow-Up Study Visits

The study follow-up visits will occur 6, 12, 18, and 24 months post-procedure. In addition, subjects may be requested to attend Follow-up Visits once a year after the twenty-four month follow-up for up to ten years.

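### The symptom limb of healing makes a tooth a primary success on a reduction at one visit, with no minimum change, no rule for combining signs and no confirmation

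*Combined protocol and SAP*

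**What the plan says.** The Synopsis (Section 1.0) sets the primary endpoint as "Subject teeth in the Treatment Complete cohort that are healed or are healing at the twenty-four month follow-up visit". It then gives two routes to success.

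- Healed: "Healed is defined by absence of a radiographic indication of apical periodontitis (PAI <3) and absence of clinical signs and symptoms".
- Healing: "Healing is defined by a reduction of radiolucency (if radiolucency is present at Baseline) and/or reduction of clinical signs and symptoms". The symptom limb, with its condition, reads "reduction of clinical signs and symptoms (if clinical signs and symptoms are present at Baseline".

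Section 3.1 repeats these definitions. Section 13.4 bases the primary analysis on healing at 24 months, with a proportion and an exact 95% confidence interval, and adds no definition.

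Percussion and palpation are graded None, Mild, Moderate or Severe at Baseline (7.4.4) and at follow-up (7.17.2). The lowest positive grade is "Mild (+): Little discomfort, but may be noticeable by the patient". Entry sets no severity floor; for the tooth's condition Section 5.1 asks only that "The subject tooth is indicated for root canal therapy". Blinding is described for the radiograph readers ("Independent reviewers will be blinded to the site, subject, and visit when completing the PAI score") and not for the clinical grades. On timing, "The study follow-up visits will occur 6, 12, 18, and 24 months post-procedure", so an 18-month assessment already exists.

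Section 2.3 says future endodontic studies should define success as PAI 1 or 2 with no clinical signs or symptoms, and should present complete and incomplete healing separately.

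**The concern.** The symptom limb opens when a sign is scored present at Baseline and can be met by the smallest possible fall at one later visit. On a four-grade subjective scale, a tooth graded Mild at entry and None at month 24 may have changed, or may have been graded differently twice. Teeth qualify because they scored positive at Baseline, so some were over-graded that day and will tend to score lower later without true change. That is regression to the mean.

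A control arm graded in the same way would carry the same noise. Here the result is set against a fixed 70% from the literature (Section 13.1), and nothing in the plan allows for it. Because of the and/or, a tooth with an unchanged lesion can be a primary success on a one-grade fall in tenderness. What is at stake is whether a pooled rate above 70% can be read as healing in the sense of Section 2.3.

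**Working it through.** **1. The plan's own figure.** Inputs from Section 13.1: n = 86, null 0.70, alternative 0.85, two-sided exact binomial test at 5%. The upper critical value is 69 of 86 (80.2%). P(X ≥ 69 | 0.70) = 0.0223; adding the lower tail gives a two-sided size of 0.0447. P(X ≥ 69 | 0.85) = 0.914. The stated power of about 90% reproduces.

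**2. A hand calculation for one sign.** Assumptions, not in the documents: the true grade does not change; true grades at entry are Mild, Moderate and Severe in equal thirds; each grading is wrong by one step with probability 0.10 (half up, half down; from Severe always down). The chance of an observed positive Baseline grade followed by a lower 24-month grade is:

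- true Mild: 0.90 × 0.05 + 0.05 × 0.95 = 0.0925
- true Moderate: 0.90 × 0.05 + 0.05 × 0.95 = 0.0925
- true Severe: 0.90 × 0.10 = 0.0900

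The mean is 0.0917. The chance of a positive Baseline grade is 1 − 0.05/3 = 0.9833, so the false-success share is 0.0917/0.9833 = 9.3%. Requiring None at month 24 instead gives (1/3 × 0.95 × 0.05)/0.9833 = 1.6%.

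**3. How far the share moves with the assumptions.** With one-step misgrading over four severity mixes, one sign gives 5-7% at 5% misgrading, 9-13% at 10%, 17-23% at 20% and 31-38% at 50%. If a fall in either of two signs counts (three mixes), the share is about 10%, 18-19% and 31-33% at 5%, 10% and 20% misgrading, and 46-49% at 40%.

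A second model uses a normal latent severity for each of two signs (correlation 0.5), independent grading error with reliability r, no true change, and 400,000 teeth per scenario. The table gives the percentage counted as healing among teeth positive at Baseline, for r = 0.80 / 0.90 / 0.95. Repeat runs agree within about 1 point.

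| Combination rule | Cuts 0.5, 1.0, 1.6 | Cuts −0.5, 0.3, 1.0 | Cuts −1, 0, 1 |
|---|---|---|---|
| Either sign lower | 56 / 45 / 35 | 46 / 36 / 27 | 40 / 31 / 22 |
| Summed grade lower | 46 / 39 / 31 | 35 / 30 / 24 | 31 / 25 / 20 |
| Every sign present lower, none higher | 34 / 27 / 21 | 16 / 12 / 8 | 9 / 6 / 4 |

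At r = 0.70 the top-left cell becomes 62%. The overall span is therefore roughly 5% to 60%.

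**4. What confirmation and absence each achieve.** At r = 0.90 with the first set of cuts, requiring the reduction at both 18 and 24 months lowers the either-sign share from 45% only to 29%, because both comparisons share one Baseline error. Requiring both signs to be None at month 24 gives 16% (5% with the second set of cuts). Requiring None at both visits gives 8% (2%).

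**5. Illustration at trial level.** Suppose 70% of teeth are truly healed and 30% are unchanged. Let s be the proportion of that 30% symptomatic at Baseline and f the false-success share. Ignoring false failures, the observed rate is p = 0.70 + 0.30 × s × f.

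| s | f | p | P(X ≥ 69 of 86) |
|---|---|---|---|
| any | 0 | 0.700 | 2.2% |
| 0.5 | 0.10 | 0.715 | 4.3% |
| 1 | 0.10 | 0.730 | 7.9% |
| 0.5 | 1/3 | 0.750 | 16.0% |
| 0.5 | 1/2 | 0.775 | 32.3% |

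**The case against.** A reader might infer from the larger simulated values that a third to a half of unchanged symptomatic teeth will be scored as successes. The documents do not support a figure of that kind. They give no reliability, severity mix or number of symptomatic teeth. They also do not say that a fall in one sign is enough: the wording is plural and silent on how signs combine. Under the strictest combination rule the share can be as low as 4%. The gap is an undefined rule, and the most permissive reading should not be presented as the sponsor's.

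A reader might also infer that noise can only help the device. That is true only for teeth with no real change. A sign-free tooth graded Mild at month 24 is no longer healed, and if it was sign-free at Baseline the symptom limb is closed to it. One simulation of clinical signs alone, assuming 70-90% of teeth truly improve and reliability of 0.80 to 0.95, gave false successes of 1 to 6 points, false failures of 0.4 to 8 points, and a net effect from about −5.5 to +3.5 points. This objection stands.

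Section 13.0 also leaves analysis details to a statistical analysis plan, and the literature report behind the 70% is not in the text available, so whether the comparator counts partial healing cannot be checked. Neither point answers the concern: the endpoint definition is in the protocol itself, and it departs from the advice in Section 2.3.

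**Conclusion.** The point holds as a defect of definition. As written, a partial, unconfirmed reduction in signs at one visit, without radiographic improvement, is a primary success. That departs from Section 2.3 and makes the pooled rate hard to read against a fixed 70%. This part needs no assumed noise rate.

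The size is conditional. Roughly 5% to 60% of truly unchanged symptomatic teeth would count as healing, depending on reliability, severity mix and combination rule. In the illustration, even a 10% share raises the upper-tail error from 2.2% to 4-8%, and a share of one third to one half raises it to 16-32% if half of the unhealed teeth are symptomatic. These figures assume that exactly 70% are truly healed, that the rest are unchanged, and that there are no false failures. They show what the rule permits and do not predict this trial's result. The definition should be tightened before the 24-month data are analysed.

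**What to change.** In the Synopsis and Section 3.1, name the qualifying signs (percussion, palpation, swelling, sinus tract), and let the symptom limb count only if all are None or absent at the 24-month visit. Use the 18-month visit (12-month if that was missed) as confirmation, at least as a pre-specified sensitivity analysis. In Section 13.4, report healed and healing as separate proportions, each with an exact 95% confidence interval. Apply the same list of signs to the healed definition. The symptom limb then adds only teeth that are free of those signs but still at PAI 3 or above, and separate reporting makes them visible.

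The change needs wording only, since the assessments are already scheduled. Its costs should be stated:

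- The success rate will be lower.
- Residual grading error will reject some improved teeth through this limb. If both signs of an improved tooth sit 0.5 latent SD below the Mild cut, the rejected share at month 24 is 1 − Φ(0.5/√(1−r))², which is 25%, 11% and 3% at r = 0.80, 0.90 and 0.95. Requiring both visits (fourth power) makes it 43%, 21% and 5%. Teeth that improve further are rejected less often.
- If confirmation is mandatory, teeth that improve between months 18 and 24 are not counted, and a second required visit adds missing data, which Sections 13.2 and 13.7 already treat inconsistently. This favours confirmation as a sensitivity analysis.
- Section 7.16 recognises tenderness after crown placement, so the definition must say how such tenderness is scored.

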### 2.0 INTRODUCTION AND RATIONALE

### 2.1 General Background

Over 15 million cases of root canal therapy (RCT) are performed each year in the United States. If performed effectively, RCT can be the best treatment for a necrotic or irreversibly inflamed pulp. However, the current methodologies rely on technologies invented over 200 years ago and which are not only inefficient, but also are associated with several procedural and safety issues, such as leaving uninstrumented recesses, root weakening, ledge formation, perforations, over-instrumentation, instrument separation, extrusion of debris into the periapical tissue, and periapical extrusion of sodium hypochlorite. The introduction of the Sonendo GentleWave device may substantially reduce and, in some cases, eliminate the risks associated with a traditional root canal procedure.

#### 2.2 Drawbacks of Current Methods in Root Canal Therapy

After more than two centuries, modern endodontics still suffers from a number of procedural and safety issues that diminish the achievement of consistently successful outcomes in RCT. Some of these issues are briefly discussed below.

## 2.2.1 Leaving Uninstrumented Recesses

The conventional method of RCT does not uniformly and completely clean canals. Although metallic files (e.g nickel titanium) are flexible and conform to the curvature of a canal, they still do not touch all root canal surfaces as they are fundamentally rigid, round pieces of metal. Therefore, it is typical for at least 35% (and as high as 50%) of the canal surface to be passed over during instrumentation. This bypass, combined with the inefficiency of current irrigation methods, results in 40% to 60% of canals still yielding positive cultures after instrumentation and irrigation with different sodium hypochlorite (NaOCI) concentrations.

Another factor increasing the chance of leaving uninstrumented recesses is the canal curvature. This issue is specifically the case for long and narrow oval canals (ratio of major/minor canal diameters is greater than 2.0). Hulsmann et al. studied the RCTs performed on mandibular molars using two different rotary instruments. They found that 81-88% of the canals will be left with some degree of uninstrumented recesses. Vaudt et al. compared the performance of the Alpha System and ProTaper Universal with manual techniques and found that in 80% of the manually treated curved mesial canals of mandibular molars more than 25% of the canal surface remained uninstrumented.

## 2.2.2 Root Weakening

Instrumentation increases the diameter of the root canals to allow for proper flow of irrigant and obturation. This filing also removes dentin from canal walls, which weakens the root. From a strength and materials perspective, it is straightforward that removing the natural dentinal structure reduces the tooth strength. Consequently, RCT may be associated with some level of root weakening. A high price is paid solely due to the inability of the current methodology to remove the pulp and the bacteria without damaging and weakening the natural structure of the tooth. This adverse treatment effect becomes even more pronounced when the canal crosssectional shape deviates from a circular shape and when canals are curved. For instance, long oval shapes are generally impossible to completely instrument without perforating or severely weakening the roots. While nature is elegant, it rarely forms perfectly straight and wide canals that are well-situated to the equipment and technical limitations of the current standard of care.

## 2.2.3 Ledge Formation

Ledge formation is among the most commonly observed procedural errors during root canal instrumentation. It is defined as a deviation from the original canal curvature, where communication with the apical constriction is lost. The presence of a ledge might exclude the possibility of achieving an adequately shaped canal that reaches the ideal working length, which may result in incomplete instrumentation and disinfection of the root canal system, as well as incomplete filling of the canal. The root canal space apical to the ledge is difficult to adequately clean and shape; therefore, ledges frequently result in persistent periapical pathosis after the endodontic treatment. Consequently, there is a causal relationship between ledge formation and unfavorable endodontic treatment outcomes. Some of the reported frequencies of ledge formation include: 11% by Bergenholtz et al., 10% by Stadler et al., 46% by Greene and Krell, 52% by Kapalas and Lambrianidis, and 25% by Eleftheriadis and Lambrianidis. In one study, endodontists performed RCTs and reportedly created ledges in 33% of previously untreated canals and 41% of endodontic retreatment cases.

## 2.2.4 Perforation

Root perforations are shown to be one of the eminent causes of endodontic failures. They are artificial openings in root walls created by boring, piercing, or filing that result in a communication between the pulp space and periodontal tissues. These openings may cause secondary periodontal involvement and eventual loss of the tooth. latrogenic perforations are often due to insufficient attention to the details of internal anatomy and a failure to consider anatomic variations. They may also be due to lack of information on the canal anatomy and morphology, as the dental radiographs only provide a buccolingual view of the tooth. Accidental root perforations, which may have serious implications, occur in approximately 2–12% of endodontically treated teeth. Bacterial infection emanating either from the root canal or the periodontal tissues, or both, prevents healing and promotes inflammatory sequels where the supporting tissues have been exposed. This bacterial exposure may be followed by painful conditions, abscesses, and fistulae, including bone resorption processes. Once an infectious process has established itself at the perforation site, prognosis for treatment is precarious and the complication may prompt extraction of the affected tooth.

## 2.2.5 Penetration of Instruments into the Periapical Tissue

Another commonly occurring iatrogenic error is the penetration of the endodontic instruments beyond the apical foramen, which results in damage to the periapical tissue and triggers foreign body immunological response (Figure 1). It is well accepted and proven that instrumentation beyond the apical foramen should be avoided as it reduces the success rate. In clinical

practice, one of the major difficulties is that the apical constriction cannot be detected radiographically. According to ElAyouti et al., the endodontic instruments penetrate beyond the apical foramen in 25% of cases. In 10% of cases, the file penetration is greater than 1mm. They argued that this penetration is mainly due to the fact that the apical foramen is located laterally in 78% to 93% of the cases. ElAyouti et al. determined that a seemingly accurate working length (ending radiographically 0 to 2mm short of the radiographic apex) frequently resulted in instrumentation beyond the apical foramen. Even the advent of apex locators has not been able to resolve the issue as the function of apex locators is consistent in only 85% of patients.

Figure 1: The photograph of the extracted tooth illustrates the file beyond the apical foramen. Examiners indicated that the file was at the correct radiographic working length. This penetration error is an example of an underestimation of the actual working length distance, causing the file to be too long.

